6.8. Other Safety Assessments

6.8.1. Best-Corrected Visual Acuity

Best-corrected visual acuity (BCVA) measurement will be performed in each eye at all study visits with the logMAR eye chart using the subject's best corrective lens prescription eyeglasses or trial frame lenses, if applicable. The subject's BCVA must be determined (via refraction) if corrected or uncorrected visual acuity is not logMAR 0.0 (equivalent to 20/20). This refraction must be used for all VA assessments for the duration of the study. The subject must wear the same glasses/trial frame, if applicable, at each visit. Ambient room lighting should be consistent for a given subject throughout the study period. Consult the Study Reference Manual for specific details regarding the evaluation procedures.

6.8.2. Biomicroscopy and External Eye Exam

A slit-lamp examination will be conducted at each study visit to assess the anterior ocular structures, including lid, cornea, conjunctiva, anterior chamber, iris, lens, and posterior capsule (if pseudophakic). Abnormalities will be documented. Consult the Study Reference Manual for specific details regarding the evaluation procedures.

6.8.3. Investigational Product Comfort Assessment

Subjects will rate the comfort of IP instillation according to the following 4-point scale:

- 0 = No discomfort
- 1 = Mild discomfort
- 2 = Moderate discomfort
- 3 = Severe discomfort

6.9. Screen Failures

A screen failure is a subject who has given informed consent but failed to meet the inclusion criteria or met at least 1 of the exclusion criteria, and has not been randomized into the study. Based on Investigator discretion and Sponsor approval, subjects who initially failed to meet the inclusion/exclusion criteria may be rescreened at a later time if their eligibility status has changed. The subject will retain the same subject identification number that he/she was assigned at the first screening.

6.10. Subject Withdrawal Criteria

The following are the criteria for considering withdrawal from the study:

- Withdrawal of subject consent. The subject may request for any reason at any time to be withdrawn from the study.
- Investigator/Sponsor decision (prohibited medication, compliance, etc.)
- The Sponsor terminates the study.

If a subject withdraws from the study, the reason for withdrawal will be recorded in the eCRF.

If a study subject fails to attend a study visit at any point during the study period, every effort should be made to keep the subject in the study and conduct all study visits as scheduled; all attempts to contact the subject must be documented. If the subject relocates during the study period, the CRO should be contacted to determine if there is a possibility that the subject could continue at another clinical site.

6.11. Appropriateness of Measurements

The efficacy and safety assessments in this study are standard for ophthalmologic investigations, and their reliability, accuracy, and relevance is well established. Collection of AEs to monitor drug safety is standard in clinical studies.

7. STUDY ACTIVITIES

Table 1 provides a tabular summary of all scheduled visits and procedures to be performed during the clinical study.

7.1. Visit 1 (Day -14 ± 2 /Screening Visit)

Procedures performed at Screening, Visit 1/Day -14 \pm 2 will include the following:

- Obtain written informed consent
- Inclusion/exclusion criteria
- Demographics
- Medical and ocular history
- Concomitant medication review
- Urine pregnancy test (women of childbearing potential only)
- SANDE
- BCVA (logMAR)
- Biomicroscopy/external eye exam
- TBUT
- Corneal fluorescein staining
- Anesthetized Schirmer's test
- Re-review inclusion/exclusion criteria
- Dispense run-in medication/provide instruction on administration/in-clinic administration/evaluate administration
- AE assessment

Eligible subjects must have daily symptoms of DED for ≥ 6 months, a total score ≥ 40 and ≤ 70 on the SANDE questionnaire, history of artificial tear use in the 30 days prior to Screening, TBUT ≤ 6 seconds in both eyes, and anesthetized Schirmer's test tear volume ≥ 3 mm and <10 mm in both eyes.

7.2. Treatment Period (Day 1 to Day 56 ± 4)

7.2.1. Visit 2 (Day 1/Confirmatory and Baseline/Randomization Visit)

Procedures performed at Visit 2/Day 1 include:

- Concomitant medication review
- SANDE
- Individual symptom assessment (VAS)
- IP comfort assessment

- BCVA (logMAR)
- Biomicroscopy/external eye exam
- TBUT
- Corneal fluorescein staining
- Review inclusion/exclusion criteria
- Randomize eligible subjects
- Dispense IP/provide instruction on administration
- Self-administration of first dose of randomized IP in the clinic
- AE assessment
- Run-in medication accountability

7.2.2. Visit 3 (Day 14 ± 2)

Procedures performed at Visit 3/Day 14 ± 2 include:

- Concomitant medication review
- SANDE
- Individual symptom assessment (VAS)
- IP comfort assessment
- BCVA (logMAR)
- Biomicroscopy/external eye exam
- TBUT
- Corneal fluorescein staining
- AE assessment

7.2.3. Visit 4 (Day 28 ± 2)

Procedures performed at Visit 4/Day 28 ± 2 include:

- Concomitant medication review
- SANDE
- Individual symptom assessment (VAS)
- IP comfort assessment
- BCVA (logMAR)
- Biomicroscopy/external eye exam
- TBUT
- Corneal fluorescein staining

- Dispense IP/provide instruction on administration
- IP accountability
- AE assessment

7.2.4. Visit 5 (Day 56 ± 4) or Early Termination Procedures

Procedures performed at Visit 5/Day 56 ± 4 include:

- Concomitant medication review
- SANDE
- Individual symptom assessment (VAS)
- IP comfort assessment
- BCVA (logMAR)
- Biomicroscopy/external eye exam
- TBUT
- Corneal fluorescein staining
- Urine pregnancy test (women of childbearing potential only)
- AE assessment
- IP accountability

8. QUALITY CONTROL AND ASSURANCE

Silk Technologies and/or their contracted agents utilize standard operating procedures (SOPs) designed to ensure that research procedures and documentation are consistently conducted/prepared to the highest quality standards. These SOPs require compliance with FDA regulations and the International Council for Harmonisation (ICH) Good Clinical Practice (GCP) guidance.

The study will be monitored by CRAs/monitors to verify that the rights and well-being of human subjects are being protected, the reported data are accurate, complete, and verifiable, and that the conduct of the study is in compliance with the currently approved protocol, with ICH GCP, and with the applicable regulatory requirements.

To ensure compliance with GCP and all applicable regulatory requirements, Silk Technologies or its agents may conduct a quality assurance audit at any time during or after completion of a study. The Investigator will be given adequate notice if s/he is selected for an audit. The audit will include, but is not limited to: a review of all informed consent forms, medical records, and regulatory documentation; an assessment of study conduct and protocol compliance; and a review of the study materials receipt, storage, and administration. At the conclusion of an audit, the auditor will conduct a brief meeting with the Investigator to review the findings of the audit.

9. STATISTICS

9.1. General Considerations

This is a Phase 2, multicenter, randomized, double-masked, vehicle-controlled, parallel group study to evaluate the safety and efficacy of 1.0% SDP-4 ophthalmic solution in subjects with DED.

Subjects with DED are planned to be randomized to SDP-4 (1.0%) or vehicle in a 1:1 ratio, with 70 subjects randomized to each group.

A biostatistician will perform statistical analyses as agreed with the Sponsor according to the Statistical Analysis Plan (SAP).

All continuous study assessments will be summarized by treatment and visit (as applicable) using descriptive statistics (n, mean, median, standard deviation, minimum, and maximum). All categorical study assessments will be summarized by treatment and visit (as applicable) using frequency counts and percentages.

All study data will be listed by treatment, subject, and visit (as applicable).

The unit of analysis for efficacy will be the study eye.

Efficacy analysis will be conducted on the intent-to-treat (ITT) population (primary efficacy analysis) and the per protocol (PP) population (secondary efficacy analysis). Safety analyses will be performed using the safety analysis population. Definitions for the analysis populations may be found in Section 9.3.

9.2. Determination of Sample Size

Based on results from SDP-4-CS201, a treatment difference of 12.2 units SANDE total score mean change from baseline at Day 56 was observed in the subgroup population meeting the Total SANDE score \geq 40 and \leq 70. A sample size of 70 subjects per treatment group will have 84.5% power to detect above observed treatment difference assuming observed standard deviations of the two groups (i.e., 22.7 and 25.4) using a two-sided t-test with a 0.05 significance level.

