A detailed Statistical Analysis Plan (SAP) will be finalized prior to database lock.

General Considerations

All continuous study assessments will be summarized by treatment and visit (as applicable) using descriptive statistics (n, mean, median, standard deviation, minimum, and maximum). All categorical study assessments will be summarized by treatment and visit (as applicable) using frequency counts and percentages.

All study data will be listed by treatment, subject, and visit (as applicable).

The unit of analysis for efficacy will be the study eye.

Sample Size Rationale

Based on results from Study SDP-4-CS201, a treatment difference of 12.2 units SANDE total score mean change from baseline at Day 56 was observed in the subgroup population meeting the Total SANDE score \geq 40 and \leq 70. A sample size of 70 subjects per treatment group will have 84.5% power to detect above observed treatment difference assuming observed standard deviations of two groups (i.e., 22.7 and 25.4) using a two-sided t-test with a 0.05 significance level.

Analysis Populations

The intent-to-treat (ITT) population will include all randomized subjects who received IP.

The per protocol (PP) population is a subset of the ITT population, which will include all subjects who complete the study without major protocol deviations.

The safety population will include all subjects who received IP.

Table 1Schedule of Visits and Examinations

	Visit 1 Day -14 ± 2 Screening	Visit 2 Day 1 Baseline/ Randomization	Visit 3 Day 14 ± 2 Treatment	Visit 4 Day 28 ± 2 Treatment	Visit 5 Day 56 ± 4 Treatment/End of Assessments
Informed consent	Х				
Review inclusion/exclusion criteria	X	Х			
Demographics	Х				
Medical and ocular history	Х				
Concomitant medication/review	Х	X	Х	Х	Х
Urine pregnancy test	Х				Х
SANDE	Х	Х	Х	Х	Х
VAS assessment of individual symptoms		Х	Х	Х	Х
IP comfort assessment		Х	Х	Х	Х
Best-corrected visual acuity	Х	Х	Х	Х	Х
Biomicroscopy and external eye exam	Х	Х	Х	Х	Х
Tear break-up time	Х	Х	Х	Х	Х
Corneal fluorescein staining by zone	Х	Х	Х	Х	Х
Anesthetized Schirmer's test	Х				
Dispense and provide instruction on administration/evaluate administration of run-in (vehicle)	Х				
Randomization		Х			
Dispense and provide instruction on administration investigational product (IP)		Х		х	
Adverse event assessment	X	X	Х	Х	Х
Run-in medication or IP return and accountability		Х		Х	Х

IP = investigational product; SANDE = Symptom Assessment in Dry Eye; VAS = visual analogue scale

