9.5.3. Efficacy Analyses

The primary efficacy endpoint (SANDE) will be summarized using continuous summary statistics by treatment group and visit. The primary analysis will utilize a repeated measures mixed model where the dependent variable is the change from baseline score, treatment group is a fixed effect, baseline score is a covariate, and visit is a repeated measure on subject. The repeated measures mixed model is utilized to account for the effect of missing data under the assumption that the data are missing at random. Least squares means will be used to test SDP-4 to vehicle. Sensitivity analyses for the primary endpoint will be performed using last observation carried forward (LOCF) as well as observed data only.

The planned analyses for all efficacy outcomes will be described in detail in the SAP, which will be finalized prior to database lock.

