1.2 Study Design

This is a Phase 2, multicenter, double-masked, randomized, vehicle-controlled, dose-response, parallel-group study designed to evaluate the ocular and systemic safety and efficacy of SDP-4 ophthalmic solution in subjects with moderate to severe DED in both eyes (OU) over a 12-week (84-day) treatment period.

Subjects will be randomized to 1 of 3 concentrations (0.1%, 1.0% and 3.0%) of SDP-4 Ophthalmic Solution or vehicle in a 1:1:1:1 ratio, with 75 subjects randomized to each group in parallel. All investigational products (IP) (SDP-4 concentrations and vehicle) will be provided in single-use dose (SUD) containers seal packed into foil pouches.

The IP will be administered via topical ocular instillation, one drop per eye, twice daily (BID) for 12 weeks (84 days). Both eyes will be treated. A 2-week screening/run-in period on BID vehicle will precede the 12-week randomized treatment period.

Subjects must have a Symptom Assessment in Dry Eye (SANDE) total score of \geq 40 at Visit 1/Screening and Visit 2/Day 1 to enter the trial. The study will consist of 7 clinic visits, 2 visits during the screening period and 5 on treatment visits: Visit 1 (Day -14 ± 2/Screening Visit), followed by a 2-week run-in on BID vehicle, Visit 2 (Day 1/Confirmatory and Randomization Visit), Visit 3 (Day 7 ± 2), Visit 4 (Day 14 ± 2), Visit 5 (Day 28 ± 2), Visit 6 (Day 56 ± 4) and Visit 7 (Day 84 ± 4/End of Study Assessments).

If a subject complains of persistent dry eye symptoms, the site may provide the subject with unpreserved artificial tears (provided by the Sponsor), to be used

only if necessary. The subject must return all used and unused artificial tears at each visit so the site can conduct accountability to assess the use of artificial tears. Artificial tears may not be used within 2 hours prior to any study visit.

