1.3 Sample Size Estimation

A sample size of 70 subjects per treatment group will have 80% power to detect a treatment difference of 11.7 units in SANDE total score and 1.2 seconds in TBUT at Visit 7/Day 84 using a t-test with a 0.05 two-sided significance level. This calculation is based on the assumptions shown in Table 1. Sample size was derived using assumptions based on expected SANDE and TBUT values, TBUT being one of several secondary outcomes to be analyzed. Over-enrollment of 5 subjects per group/20 subjects per study is planned to account for discontinuations.

•		
Assumptions	SANDE	TBUT
Test significance level, α	0.050	0.050
1 or 2 sided test	2	2
Difference in means, μ_1 - μ_2	11.684	1.192
Common standard deviation	24.500	2.500
Effect size, $\delta = \mu_1 - \mu_2 /\sigma$	0.477	0.477
Power (%)	80	80
n per group	70	70

Table 1. Sample Size Estimation

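### Does the 84.5% power in Protocol 9.2 mislead, since it counts all 70 randomized per arm as evaluable and takes the 12.2-unit subgroup difference at face value?

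*Protocol*

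**What the plan says.** Protocol 9.2, repeated in the synopsis, gives every input. For the effect, it reports that "a treatment difference of 12.2 units SANDE total score mean change from baseline at Day 56 was observed in the subgroup population" with total SANDE between 40 and 70 in SDP-4-CS201. The SDs are 22.7 and 25.4, and the synopsis introduces them with "assuming observed standard deviations of two groups". The test is a two-sided t-test at 0.05, and the result is "A sample size of 70 subjects per treatment group will have 84.5% power to detect above observed treatment difference".

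Protocol 9.1 fixes the number randomized, "with 70 subjects randomized to each group", so the n in the power statement is the n randomized. No dropout rate, over-enrollment or replacement of subjects is mentioned.

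The protocol does expect some loss. Section 7.2.4 covers Visit 5 "or Early Termination Procedures", and Section 9.5.3 says: "The repeated measures mixed model is utilized to account for the effect of missing data". That model has baseline score as a covariate. The ITT population (9.3.1) is everyone randomized who received product.

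The supplied SAP describes a different design: four arms, 84 days, Final Version 1.0 dated June 2019, before the March 2020 protocol. Its Section 1.2 describes a trial "with 75 subjects randomized to each group in parallel", while its Section 1.3 powers on 70 and explains: "Over-enrollment of 5 subjects per group/20 subjects per study is planned to account for discontinuations".

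**The concern.** Two features of the 84.5% draw the eye.

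First, it is reached only if all 70 randomized per arm contribute at Day 56. The other plan in the file also powers on 70 per group but randomizes 75 to protect that number. This protocol keeps the 70 and has no such margin.

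Second, 12.2 units is an observed subgroup result, and the same SANDE window is now the entry criterion. Effects chosen after seeing the data tend to shrink on repetition. The protocol does not give the concentration, the subgroup size, a confidence interval, or whether the subgroup was planned. The supplied SAP, if it is the plan of the previous trial, had a Day 84 primary endpoint and planned no subgroup analyses.

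As 84.5% is the only power figure given, it could be read as what 140 randomized subjects will deliver. If the real power were much lower, the sponsor could misjudge the chance of a false negative.

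**Working it through.** **Inputs.** Difference 12.2; SDs 22.7 and 25.4; 70 per arm; two-sided 0.05 (all Protocol 9.2). The loss rates and alternative effects below are assumptions, except 5/75 = 6.7%, which is the SAP's allowance for its longer trial.

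**1. Reproduce the stated figure.**
SD = √((22.7² + 25.4²)/2) = 24.09.
Standard error = 24.09 × √(2/70) = 4.07.
Noncentrality = 12.2/4.07 = 3.00; critical t on 138 df = 1.977.
Power from the noncentral t = 84.51%; the unequal-variance version gives 84.50%. The stated 84.5% is correct.

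**2. Loss alone, difference 12.2, completers-only t-test.**

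| Evaluable per arm | Loss | Power |
|---|---|---|
| 70 | 0% | 84.5% |
| 66 | about 5% | 82.3% |
| 65 | about 7% | 81.7% |
| 63 | 10% | 80.5% |
| 59 | about 15% | 77.9% |

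The SAP's allowance (70 × 70/75 = 65.3 per arm) costs about 3 points. Restoring the full 84.5% would take 75 randomized per arm, or 10 more subjects. Also, 63 evaluable is the smallest n per arm with 80% power, and 63/0.90 = 70. So 70 randomized supports 80% power with 10% loss, although the protocol does not put it that way.

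**3. What the primary model gives back.** The table discards early leavers and ignores baseline. Adjusting for a baseline correlated r with the change score multiplies the SD by √(1 − r²) and uses 2n − 3 df. The documents do not give r.

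| r | Power, 65 per arm | Power, 63 per arm |
|---|---|---|
| 0.1 | 82.1% | 80.9% |
| 0.2 | 83.3% | 82.1% |
| 0.3 | 85.2% | 84.1% |

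The values of r that restore 84.5% are 0.27 at 65 per arm and 0.32 at 63. The entry window limits r. If baseline scores were spread evenly over 40 to 70, their SD would be 30/√12 = 8.66, so r is about (8.66/24.09) × slope = 0.36 × slope of change on baseline. Full recovery by this route therefore needs a steep slope (about 0.75 at 65 per arm, 0.89 at 63), and partial recovery is more likely. Day 14 and Day 28 scores from subjects who leave early add further information that this calculation leaves out.

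**4. Effect alone, 70 evaluable per arm.**

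| True difference | Power |
|---|---|
| 14 | 92.7% |
| 12.2 | 84.5% |
| 11.7 (SAP planning value) | 81.4% |
| 10 | 68.4% |
| 8 | 49.7% |

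The 8-unit row says little about this plan. The smallest significant observed difference is 1.977 × 4.07 = 8.05, and power at the significance threshold is about 50% at any sample size (50.3% at 35 per arm, 50.0% at 500).

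**5. Precision of 12.2.** The subgroup size is not given. If the comparison had 75 per group (the SAP's full planned arm), the 95% interval would be 12.2 ± 7.8, or 4.4 to 20.0. At an assumed 40 per group it would be 1.5 to 22.9. Values well above 12.2 are as compatible with it as values well below.

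**The case for a change.** The strongest case for a change is that it costs only text. State that 84.5% needs 70 evaluable per arm, identify where 12.2 came from, and tabulate power at smaller effects. At 10 units the trial misses a real difference about 32% of the time even with no loss (100 − 68.4), and selection of the subgroup makes some shrinkage likely.

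Part of this stands. The number randomized is used as the number analysed without saying so, no range is given, and a reader would be better informed with both. The provenance of 12.2 is thin.

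Three things do not stand. The effect assumption is not hidden: 9.2 calls it the observed difference and names the subgroup. The 84.5% is not an upper limit either, since the true effect may exceed 12.2 and the primary model may be more efficient than the t-test. Nor does a single power figure obscure what a non-significant result means. That is read from the trial's own confidence interval, whose half-width with 70 per arm and these SDs would be 8.05 units.

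**Conclusion.** No change follows. The 84.5% is correct for its stated inputs, and the source of the effect is disclosed. The omission that remains is an attrition allowance. It is worth about 2 to 4 points by t-test at 5% to 10% loss, and less once the planned model's baseline covariate and partial follow-up are counted. Power at 12.2 units stays above 80% up to 10% loss. At 15% loss the t-test figure is 77.9%, but nothing in the documents points to loss of that size over 56 days.

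Sensitivity to the true effect is larger, but an unknown effect is a feature of every Phase 2 plan. The alternatives of 8, 10 or 14 units are the reviewer's choice and cannot be ranked from these documents. Adding them would leave N = 140, the design, the primary model and the reading of the result as they are. If the sponsor revises 9.2 for another reason, one sentence on evaluable n, and a range with effects both above and below 12.2, would be a courtesy to readers.

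This rests on loss near the assumed 5% to 10%, on data missing at random as Protocol 9.5.3 assumes, and on SDs close to those quoted.

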9.3. Analysis Populations

9.3.1. Intent-to-Treat (ITT) Population

The ITT population will include all randomized subjects who received IP. This population will be the primary population for efficacy analyses and will be used to summarize all efficacy variables and will summarize subjects as randomized.

9.3.2. Per Protocol (PP) Population

The PP population is a subset of the ITT population, which will include all subjects who complete the study without major protocol deviations. This population will be the secondary population for efficacy analyses and will be used to summarize a subset of efficacy variables. The PP population will summarize subjects as treated.

9.3.3. Safety Population

The safety population will include all subjects who received IP. This population will be used to summarize safety variables and will summarize subjects as treated.

9.4. Demographics and Baseline Characteristics

Subject demographic and baseline characteristics will be summarized in tables. Summary tables will be supported with individual subject data listings.

9.5. Efficacy Endpoints and Analyses

9.5.1. Primary Efficacy Endpoint

Mean change from baseline in total SANDE score at Visit 5/Day 56

9.5.2. Secondary Efficacy Endpoints

- Mean and mean change from baseline at each visit for each of the following evaluations:
 - Corneal fluorescein staining (combined and each zone)
 - TBUT
 - Conjunctival hyperemia
 - Individual symptom VAS scores, separately for each symptom
- SANDE
 - Mean change from baseline in total SANDE score at each visit
 - Mean total SANDE score at each visit
 - Mean and mean change from baseline in each component of SANDE at each visit

